5.6 Total Number of Participants and Sites

Data from 40 participant will be required and the study would accrue 50 patients to account for an attrition rate of 20%.

The study will be conducted only at NYULH Hospitals. No subjects will be enrolled at external national or international sites.

5.7 Participant Withdrawal or Termination

5.7.1 Reasons for Withdrawal or Termination

Participants are free to withdraw from participation in the study at any time upon request. Participation of a patient in this clinical study may be discontinued for any of the following reasons:

- The patient withdraws consent or requests discontinuation from the study for any reason;
- Occurrence of any medical condition or circumstance that exposes the patient to substantial risk and/or does not allow the patient to adhere to the requirements of the protocol;
- Any AE, clinically significant adverse event, severe laboratory abnormality, intercurrent illness, or other medical condition that indicates to the investigator that continued participation is not in the best interest of the patient;
- Pregnancy during study period;

CONFIDENTIAL

- Patient failure to comply with protocol requirements or study-related procedures;
- Termination of the study by the Sponsor, the regulatory authority, FDA, or IRB.
- The participant meets an exclusion criterion (either newly developed or not previously recognized) that precludes further study participation
- Progression of osteoarthritis requiring surgical therapy
- Patients found to have osteonecrosis on pre-procedural MRI

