4.2.2 Secondary Study Endpoints Analysis

Secondary efficacy endpoints are:

- 1- WOMAC pain score at 1- and 12- months (and final 18-48 months visit) post intervention
- 2- Pain electronic VAS at 1-, 3-, and 12- months (and final 18-48 months visit) post intervention
- 3- Knee stiffness WOMAC score at 1-,3-, and 12- months (and final 18-48 months visit) post intervention
- 4- Physical function WOMAC score at 1-, 3-, and 12- months (and final 18-48 months visit) post intervention
- 5- Total WOMAC score at 1-,3-, and 12- months post intervention
- 6- Self-reported quality of life using EQ-5D-5L scale at 1-, 3-, and 12- months (and final 18-48 months visit) post intervention.
- 7- MRI findings at 3- months post intervention
- 8- Pain medication usage at 1-, 3-, and 12- months (and final 18-48 months visit) post intervention
- 9- Injection therapy requirements (hyaluronic acid or steroid) at 12- months (and final 18-48 months visit) post intervention
- 10- Physical therapy requirements at 12- months (and final 18-48 months visit) post intervention
- 11- Feasibility / technical success
- 12- Laboratory findings at 1-, 3-, and 6- months (and final 18-48 months visit) post intervention

Secondary safety endpoints are:

- 13- Number/rate, severity, and description of complications, adverse events, or poor outcomes that are secondary to the procedure, which will be summarized using counts and simple statistics (i.e., mean number of patients with complications.)

CONFIDENTIAL

5 Study Enrollment and Withdrawal

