5.2 Exclusion Criteria

An individual who meets any of the following criteria will be excluded from participation in this study:

1. Active systemic or local knee infection or;
2. Active malignancy or;
3. Life expectancy less than 12 months or;
4. Prior ipsilateral knee surgery (within 3 years of baseline visit), arthroscopic surgery (within 6 months of baseline), total or partial knee replacement regardless of timing or;
5. Ipsilateral knee intra-articular injection in the last 3 months or;
6. Rheumatoid arthritis, spondyloarthropathies, crystal disease, gout, pseudogout, or lupus;
7. Pregnant during the study period or;
8. Renal dysfunction as defined by serum creatinine > 1.6 dl/mg or eGFR < 60 on blood tests obtained within 30 days of procedure or;
9. Body weight greater than 200 Kg or;
10. Uncorrectable coagulopathy (platelet count $< 50,000$, international normalized ratio > 1.5 within 30 days of procedure; or
11. Known history of contrast allergy resulting in anaphylaxis or;
12. Known significant arterial atherosclerosis that would limit selective angiography and/or lower extremity symptoms thought to be secondary to arterial vascular disease (eg claudication, ischemic rest pain)
13. Post-traumatic knee (if trauma occurred within 12 months of baseline or was associated with fractures)
14. known avascular necrosis in the target knee
15. Contraindications to MRI such as such as claustrophobia, metallic fragment/implants, pacemaker.

CONFIDENTIAL

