5.7.2 Handling of Participant Withdrawals or Termination

If a patient withdraws prematurely from the study due to the above criteria or any other reason, study staff should make every effort to complete the full panel of assessments scheduled for the follow-up visits. The reason for patient withdrawal must be documented in the electronic case report form (eCRF). In the case of loss of follow-up, attempts to contact the patient will be made and documented in the patient's medical records. Every effort will be made to undertake protocol-specified safety follow-up procedures to capture AEs, serious adverse events (SAEs), and unanticipated problems (UPs).

Withdrawn patients can be replaced.

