6.1.7 Duration of Therapy

Treatment will be completed during one interventional session (visit 3, day 0)

CONFIDENTIAL

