8.4.4 Reporting of Pregnancy

If the subject participating in the study is found to be pregnant during the study period, participant will immediately be withdrawn from the study and IRB will be informed.

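### Section 5.7.1 does not separate withdrawal before embolization from withdrawal after it; with replacement and a completers-only analysis set, treatment failures can leave the primary analysis

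*Combined protocol and SAP*

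**What the plan says.** Section 5.7.1 opens with "Participation of a patient in this clinical study may be discontinued for any of the following reasons". What ends is participation in the study, not treatment. Among the reasons are:

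- "The participant meets an exclusion criterion (either newly developed or not previously recognized) that precludes further study participation";
- osteoarthritis progression that needs surgery;
- an adverse event, where the investigator judges that continuing is not in the patient's interest.

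Only the osteonecrosis reason is tied to a time point, the pre-procedural MRI. Section 6.1.7 confines treatment to one session on Day 0.

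The exclusion criteria (5.2) include "Ipsilateral knee intra-articular injection in the last 3 months or" and "known avascular necrosis in the target knee", as well as local knee infection and total or partial knee replacement at any time.

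Section 5.7.2 says that after withdrawal "study staff should make every effort to complete the full panel of assessments scheduled for the follow-up visits". It also asks for every effort at safety follow-up and allows withdrawn patients to be replaced. Section 7.3.6 describes one early-termination visit, without MRI. Section 8.4.4 says that on pregnancy the "participant will immediately be withdrawn from the study and IRB will be informed". Section 10.3 includes only participants who complete all follow-up visits.

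**The concern.** Stopping a course of treatment can protect a patient from further exposure. Here nothing is left to stop after Day 0, so ending study participation can only reduce what is observed.

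Several of the permitted reasons are also things the trial sets out to measure. More injection use is a failure condition in 3.1 and 10.4.1, and "Injection therapy requirements (hyaluronic acid or steroid) at 12- months" is a secondary endpoint in 4.2.2. Osteonecrosis and joint infection are listed risks in 2.4.1. Knee replacement, or surgery for progression, is a plausible course for a patient in whom the procedure has not worked.

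The trial is open label (4.1). Under Key Roles the principal investigator is one of the two operators and is responsible for the statistical analysis. The rule does not define when a newly met criterion precludes participation. For the patients most likely to be failures, scheduled visits therefore turn into best-effort visits. Replacement and the completers-only set can then take those patients out of the primary denominator. At stake is the success rate that decides whether the procedure merits further study.

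**Working it through.** **1. Overlap between withdrawal reasons and outcomes**

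| Event after Day 0 | Route to withdrawal | Where the trial counts it |
|---|---|---|
| Target-knee injection | Exclusion 5, through 5.7.1 | Failure condition (3.1, 10.4.1); 12-month endpoint (4.2.2) |
| Knee replacement or surgery for progression | Exclusion 4; also named in 5.7.1 | Not named in the success definition |
| Local knee infection | Exclusion 1, or the adverse-event reason | Listed risk (2.4.1) |
| Avascular necrosis | Exclusion 14, or the adverse-event reason | Listed risk (2.4.1) |

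**2. The plan's own figures**

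Inputs from 10.2 and 10.5: null rate 0.50, alternative 0.75, success at 16 or more of 23.

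- Significance level: P(Bin(23, 0.50) ≥ 16) = 0.0466, stated as 0.047.
- Power: P(Bin(23, 0.75) ≥ 16) = 0.8037, stated as 80.4%.
- Attrition: 23/0.8 = 28.75, so 29; 40/0.8 = 50. Both agree with the protocol.

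**3. Effect of failures leaving the analysis**

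Let *f* be the share of all treated patients who are failures, are withdrawn, and are then replaced or dropped as non-completers. With true response rate *p* and no responders withdrawn, the rate among those analysed is *p*/(1 − *f*). The documents give no value for *f*. The range runs from 0 to 20%, the planned attrition (10 of 50), which is an upper bound that takes all attrition to be withdrawn failures.

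At *p* = 0.50:

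| Assumed *f* | Rate among those analysed | P(≥ 16 of 23) | P(≥ 26 of 40) |
|---|---|---|---|
| 0 | 0.500 | 0.0466 | 0.0403 |
| 5% | 0.526 | 0.0768 | 0.0787 |
| 10% | 0.556 | 0.1259 | 0.1483 |
| 15% | 0.588 | 0.2033 | 0.2655 |
| 20% | 0.625 | 0.3196 | 0.4406 |

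The last column is added because the protocol now asks for data from 40 patients but states no cut-off for 40. The value 26 is an assumption: it is the smallest count with a one-sided level below 0.05 at a 50% rate (25 gives 0.0769).

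**4. In patient counts (assumed)**

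Of 50 treated patients, suppose 30 respond. With every failure kept, success is 30/50 = 60%. If 5 failures leave, it is 30/45 = 66.7%. If 10 leave, it is 30/40 = 75%, the rate set as the alternative hypothesis.

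**The case against.** The strongest reply is that the protocol does not abandon withdrawn patients. Section 5.7.2 asks for every effort at the full follow-up panel and at safety capture. Section 7.3.6 adds an exit visit with questionnaires. Section 8.3 records adverse events regardless of relationship and follows unresolved ones, and 8.5 follows serious events until they resolve or are judged chronic or stable. The rule is discretionary and limited to criteria that preclude participation. No section says an injection does so, and the Schedule of Activities keeps recording previous treatments through month 12, which suggests that injected patients are expected to stay.

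This reply stands against several stronger readings that a reader might infer:

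- *The data are never collected, whatever the analysis set.* Section 5.7.2 points the other way. An injection on record can also classify a patient as a failure under 3.1 without a 3-month score.
- *Harms leave follow-up.* A harm that triggers withdrawal has already been seen, and 8.3 and 8.5 keep following it.
- *The 12-month injection rate is zero by construction.* That would need every injected patient to be discontinued and the triggering injection to go uncounted. The text requires neither.
- *Contrast-related renal dysfunction is another example.* Exclusion 8 is tied to blood tests within 30 days of the procedure, and 7.2.1 lists the metabolic panel only at baseline.
- *5.7.1 names osteonecrosis as a reason after treatment.* Its explicit reason covers the pre-procedural MRI only.

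The reply does not remove the main point. Best effort is weaker than a scheduled visit, the exit visit has no MRI although MRI at 3 months is an endpoint, and 5.7.2 and 10.3 together still allow a withdrawn failure to be replaced and left out. It is fair to say that the numerical bias arises from those two provisions, with 5.7.1 supplying the patients.

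**Conclusion.** The point holds as a weakness in how 5.7.1, 5.7.2, 7.3.6 and 10.3 work together. After a completed one-session treatment, failures and some listed harms are permitted grounds for ending participation, and patients so withdrawn may be missing from the primary analysis. Data may be lost; the documents do not show that they will be.

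At a true response rate of 50%, the chance of meeting the 16-of-23 rule rises from 0.047 to 0.077, 0.126 or 0.320 if withdrawn failures make up 5%, 10% or 20% of treated patients. These figures assume that only failures are withdrawn and that none of them is counted. They shrink if responders are also withdrawn, and vanish if all treated patients stay in the denominator with failures counted as such. The shares are assumptions, so the size of the bias in this trial cannot be stated. The sponsor should fix this; it does not by itself invalidate the design.

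**What to change.** - **5.7.1:** limit the newly-met-exclusion and surgery reasons to the period before embolization. Afterwards, record an injection, knee surgery or newly met exclusion criterion as an event and keep the patient in the visits already scheduled unless consent is withdrawn, omitting assessments that cannot be done.
- **10.3:** keep all treated patients in the primary and safety denominators, and state how a treated patient without a 3-month score is classified. Whether surgery counts as non-response is a separate decision about the endpoint.
- **5.7.2:** do not replace treated patients withdrawn for outcome-related reasons.
- **5.7.1, 5.7.2, 7.3.6 and 8.4.4:** reconcile what follow-up continues after withdrawal for an adverse event or pregnancy. The clinical rule itself need not change.

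The cost is one protocol amendment with matching consent wording. No visits are added. The reported success rate may be slightly lower because more failures are counted.

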5.7.2 Handling of Participant Withdrawals or Termination

If a patient withdraws prematurely from the study due to the above criteria or any other reason, study staff should make every effort to complete the full panel of assessments scheduled for the follow-up visits. The reason for patient withdrawal must be documented in the electronic case report form (eCRF). In the case of loss of follow-up, attempts to contact the patient will be made and documented in the patient's medical records. Every effort will be made to undertake protocol-specified safety follow-up procedures to capture AEs, serious adverse events (SAEs), and unanticipated problems (UPs).

Withdrawn patients can be replaced.

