IDE for the purpose of this study was obtained from the FDA (IDE approval # G190316. Approval letter provided [attachment 2].

FDA documents of the device under investigation for approved indications and device DFU are attached to this IRB protocol [attachments 3,4].

FDA reviewed the supplement of IDE application to expand study for significant risk device proposing the addition of 21 patients. FDA has determined sufficient data to support expansion of human clinical trial; this means there are no subject protection concerns that preclude expansion of the investigation. Approved to expand study. Limit 1 US institution and 50 US subjects. [attachment G190316-S003. Letter.EPEX.APPR]

CONFIDENTIAL

This material is the property of the NYU School of Medicine and Langone Medical Center. Do not disclose or use except as authorized in writing by the study sponsor
Interventional Template Version: 12 February 2020

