10.3 Analysis Datasets

Participants who complete all follow-up visits will be included in the study.

CONFIDENTIAL

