10.5 Sample Size

The sample size was initially selected based on primary objective so that the study will have 80% power at the 5% significance level for testing the null hypothesis H_0 : $PT \leq 0.5$ against the alternative hypothesis H_A : $PT \geq 0.75$, where PT is the true proportion of patients that will manifest a positive treatment response. As a result, the study will accrue 23 patients since this sample size will endow the test with 80.4% power at a realized significance level of 0.047. with 20% attrition, the study will need 29 patients. We are requesting increase in the sample size to 40. With 20% with 20% attrition, the study will need to enroll 50 patients. The PI and sub-investigators determined that increase in the sample size is necessary to

CONFIDENTIAL

evaluate the role of GAE as a disease-modifying treatment option for knee OA. Since this current study is the only active study in the U.S collecting samples for biomarker analysis and the need for a larger sample size to evaluate changes in biomarker levels, an increase in sample size is needed.

11 Source Documents and Access to Source Data/Documents

Source data is all information, original records of clinical findings, observations, or other activities in a clinical trial necessary for the reconstruction and evaluation of the trial. Source data are contained in source documents. Examples of these original documents, and data records include: hospital records, clinical and office charts, laboratory notes, memoranda, subjects' diaries or evaluation checklists, pharmacy dispensing records, recorded data from automated instruments, copies or transcriptions certified after verification as being accurate and complete, microfiches, photographic negatives, microfilm or magnetic media, x-rays, subject files, and records kept at the pharmacy, at the laboratories, and at medical-technical departments involved in the clinical trial. It is acceptable to use CRFs as source documents. Data collected on electronic CRFs using TrialMaster are attached to this protocol (see attachment 4).

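### Section 5.7.2 lets any withdrawn patient be replaced, without a ceiling and even after embolization, although accrual of 50 already covers attrition and equals the IDE limit; with the completers-only set in 10.3 this can bias the success rate upward

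*Combined protocol and SAP*

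**What the plan says.** Section 5.7.2 ends with one sentence on replacement: "Withdrawn patients can be replaced". It gives no maximum number and no time limit, and it sets no condition on whether the patient has been treated.

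Four other places bear on it:

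- **Accrual (5.6, repeated in the Protocol Summary, 4.1, 5.4 and 10.5).** "Data from 40 participant will be required and the study would accrue 50 patients to account for an attrition rate of 20" per cent.
- **Regulatory limit (2.2, paragraphs on the IDE).** The supplement proposed adding 21 patients, and the approval is reported as "Limit 1 US institution and 50 US subjects".
- **Reasons for withdrawal (5.7.1).** One can only arise before treatment: "Patients found to have osteonecrosis on pre-procedural MRI". Others can follow treatment and point to a poor outcome: an adverse event that makes continued participation unwise in the investigator's view, and "Progression of osteoarthritis requiring surgical therapy".
- **Analysis set (10.3).** "Participants who complete all follow-up visits will be included in the study". No other analysis set is defined.

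**The concern.** Two separate matters meet in the replacement sentence.

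The first is the head count. Attrition is allowed for in the accrual figure and again, without limit, in 5.7.2. Nothing in 5.7.2 ties replacement to the 50-subject limit, so a site that replaces a withdrawn patient after the 50th enrolment would follow 5.7.2 and still pass the limit that the protocol reports.

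The second is the success rate. Follow-up runs to 12 months, while the primary outcome is read at 3 months. Under 10.3, a patient who is embolized, assessed at 3 months and then withdrawn for knee surgery is not a completer and drops out of the primary analysis. Under 5.7.2 a new patient may take that place. Patients who did badly can thus be lost from the denominator while the completer count is made up again, so no shortfall shows.

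The setting offers little protection. The study is open-label and single-arm, several withdrawal reasons rest on investigator judgement, and under Key Roles and Section 8.5 the principal investigator performs procedures, is responsible for data monitoring and statistical analysis, and acts as sponsor. The result is judged against 50% and 75% (10.2), so a shift of several percentage points could change the conclusion.

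**Working it through.** **Inputs.** 40 patients with data, 50 accrued, 20% attrition (5.6, 10.5); limit of 50 subjects and 21 added (2.2); previous size 23, or 29 with attrition (10.5); completers-only set (10.3); reference rates 0.50 and 0.75 (10.2).

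**1. The plan's own accrual figure.** Accrual = n / (1 − attrition).
- 40 / (1 − 0.20) = 50, as stated.
- The previous design also agrees: 23 / 0.80 = 28.75, rounded up to 29.
- 29 + 21 = 50, so the IDE limit equals the attrition-inflated accrual.
- Places left for replacement after full accrual: 50 − 50 = 0.

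**2. Enrolment if replacements were added after the 50th patient (conditional).**
- Expected withdrawals: 50 × 0.20 = 10.
- Each replaced once: 50 + 10 = 60.
- If replacements come out of the 50, enrolment stays at 50 and expected completers are 50 × 0.80 = 40, the stated requirement.

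**3. How likely is a shortfall that would invite replacement?** Take the number of completers as binomial with 50 patients and completion probability 1 − attrition.

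| True attrition | P(fewer than 40 completers of 50) |
|---|---|
| 10% | 0.9% |
| 15% | 12.0% |
| 20% | 41.6% |
| 25% | 73.8% |

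At the plan's own attrition rate, a shortfall is close to an even chance.

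**4. Possible effect on the success rate (assumed counts, not in the documents).** Let 40 completers include 30 responders, and let w treated patients who withdrew be non-responders. The rate among all treated is 30 / (40 + w).
- w = 0: 30/40 = 75%
- w = 5: 30/45 = 66.7%
- w = 10: 30/50 = 60%

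A second case sits near the test boundary. At one-sided 5% against a rate of 0.50, the exact binomial cut-off is 26 of 40 (level 0.040) or 32 of 50 (level 0.032). With 26 responders, 26/40 = 65% rejects the null hypothesis and 26/50 = 52% does not. These cut-offs are computed here; Section 10.2 still states the rule for 23 patients only.

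**5. Which sentence produces the shift?** The shift in step 4 arises from 10.3 alone, because the same withdrawn patients would be excluded if no one were replaced. Replacement adds new patients to the completer count. If they come from the same population, the expected rate among completers does not change. What changes is that the completer count is restored, the interval narrows around the same biased rate, and the missing treated patients are no longer visible as a shortfall.

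**The case against.** A reader might infer that 5.7.2, followed as written, breaches the IDE limit and takes enrolment to 60 or more. The documents do not support that. The sentence is permissive and never places replacements on top of the 50. Five sections fix accrual at 50, and the limit is recorded in the same protocol. On a natural reading, the ten places between 40 and 50 are where replacements come from, and nothing is exceeded. A figure of about 63 (50 / 0.80 = 62.5) needs a target of 50 completers, which the plan does not have. Nor do the documents say whether the limit counts consented, enrolled or treated subjects. If it counts treated subjects, replacing someone withdrawn before embolization uses no extra place.

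A reader might also infer that replacement is what biases the success rate. As step 5 shows, the exclusion comes from 10.3, and deleting the replacement sentence would not bring those patients back.

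On safety, 5.7.2 asks for every effort to capture events in withdrawn patients, and 8.3 requires all on-study adverse events to be documented. Replacement removes nobody from safety reporting. Only a literal use of 10.3 for the denominators in 10.4.4 would do so.

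These points stand, and they limit the claim. They do not remove it. The within-50 reading is stated nowhere, and even under it a treated patient may withdraw, leave the analysis and be replaced.

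**Conclusion.** The point holds as a gap in 5.7.2 that has consequences when read with 10.3.

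- **Enrolment.** Exceeding 50 is possible under the rule but not required by it. The size, about 10 subjects over, assumes 20% withdrawal and one replacement for each withdrawal, all after the 50th enrolment.
- **Success rate.** Sections 5.7.2 and 10.3 together let embolized patients with poor outcomes leave the denominator and be replaced. The direction is upward if treated patients who withdraw respond less often than completers, which is plausible for withdrawal because of adverse events or surgery. The size is unknown. In the illustration it runs from 0 to 15 percentage points as treated, non-responding withdrawals go from 0 to 10. If withdrawals all occurred before treatment, or responded like completers, there would be no bias.
- **Attribution.** The completers-only set is the main cause and replacement compounds it, so amending 5.7.2 alone would not be enough.

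**What to change.** Amend two sections together.

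- **5.7.2:** Only participants withdrawn before embolization on Day 0 may be replaced. Total enrolment, replacements included, does not exceed 50.
- **10.3:** All embolized participants are included in the success analysis, and those without a 3-month assessment count as non-responders. All embolized participants are included in the safety denominators.

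Changing 5.7.2 without 10.3 would leave the two sections in conflict. The rate among completers can be reported beside the main result as a sensitivity analysis.

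**Cost.** One amendment, with no new data collection.

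- The observed success rate may be lower. For example, a 75% rate among assessed patients becomes 0.75 × 0.80 = 60% if a full 20% of embolized patients lack the 3-month assessment.
- Fewer than 40 patients may have complete data, with about a 42% chance even at exactly 20% attrition. Section 10.5 sized the success test at 23 patients (80.4% power at a realized level of 0.047) and justified the rise to 40 by the biomarker work, so a small shortfall in completers falls mainly on the biomarker analyses.
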